### 5.3. Missing Data

No imputation will be performed and only analysis of complete data will be performed.

### 5.4. Additional Analytics

The evaluation of agreement between the devices will also be performed from the Cohen Kappa statistic for the primary endpoint, and each of the secondary endpoints (arrhythmias criteria one by one).

## 5.5. Safety

There will be no safety analysis, as there is no intervention in this study.

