1.1. Summary

There has been an important advance in the technology for capturing electrocardiographic signals by the Holder system in recent years. Among these advances, the following stand out: a) the miniaturization of devices; b) the possibility of capturing electrical signals by electrodes applied to the thorax without the need for cable intermediation with the recorder; c) the direct positioning of the recorder on the thoracic surface, allowing greater movement of the patient without the inconvenience of artifact records or interference in the signal line; d) possibility of transmitting electrocardiographic signals almost in real time over the computer network (internet), speeding up medical intervention in cases of high-risk arrhythmias or suspected clinical condition (syncope) being caused by such arrhythmias. No less important, it should be highlighted the speed of the preparation of the reports by the analysis software itself, which interprets the records and issues an initial report, with little or no interference from a technician or physician to edit the records. This is possible when neural networks, machine learning, and artificial intelligence are used to analyze those signals. The system in question is based on the capture of electrocardiographic recordings by Quoretech's QuoreOne recorder.

In order to reliably detect, electrocardiographic recordings obtained by QuoreOne should be compared with others already routinely used in clinical practice.

The objective of this study will be to analyze the data obtained by *QuoreOne* and compare it with those obtained by *Cardiolight* recorder analyzed by Cardios' software.

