With the advancement of technology, new signal capture systems have been developed. The possibility of applying the recorder directly to the thoracic surface eliminated the need for electrode cables. This fact not only improved the quality of the signs, but also allowed greater patient mobility, making the test better tolerated. The possibility of sending the recorded signals over the internet speeds up their interpretation. In addition, an analysis software previously trained by neural networks allows the editing of records more quickly by issuing a pre-report, facilitating the routine of the physician who will have less work to prepare the final report. With this approach, it is expected that the more exams the system analyzes, the better its performance should be, probably reaching almost the point of minimal medical interference in the final result.

In the study, which is now proposed to be carried out at the Cardiac Arrhythmias Outpatient Clinic of the Dante Pazzanese Institute of Cardiology (IDPC), Holter recordings will be performed in about 180 consecutive patients with the two systems simultaneously, the *QuoreOne* from Quoretech (system under test) and the *Cardiolight* from Cardios (conventional 24-hour Holter-system), a system that has been on the market for more than 30 years and is widely used in the country today. This approach will allow for the comparison of *QuoreOne*'s results with those of *Cardiolight*.

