## 2. STUDY METHODS

### 2.1. Study Design

This is a comparative, single-center study with consecutive inclusion of patients. Research participants will be included prospectively.

All exams will be performed at IDPC, the exams performed with the *Cardiolight* equipment will be stored both in the original file (.xcm) and in the final version of the report (.pdf). The exams performed with the *QuoreOne* equipment will be saved directly on the online report platform and in the final version of the report (.pdf). These files will be exported to an external hard drive and sent for tabbing. The parameters will be analyzed with anonymized data from the participants.

After the Holter devices are removed, the participant will be asked to answer a questionnaire about the convenience of use and functions of the *QuoreOne* device.

The Holter-type cardiac monitor is a portable ambulatory electrocardiography device. It aims to monitor the electrical activity of the heart over a prolonged period, usually twenty-four hours.

For this study, the *Cardiolight* recorder from the company Cardios, the predominant equipment in the medical practice of the IDPC, and the *QuoreOne* recorder, from Quoretech, will be used, which will be submitted to comparison.

The exams performed by the conventional system (*Cardiolight*, Cardios) will be analyzed and the reports released by physicians from the Electrophysiology Section of the IDPC. These tests will be implemented at the same time in the same patient and for the same duration. The physicians evaluating the results of one method will be the same as the physicians evaluating the results obtained by the other method, but these will be blinded to the patients' data, making it impossible to identify that the tests being evaluated are from the same patient.

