## 2.2. Randomization

This is a comparative, single-center study, where all patients included consecutively and prospectively, will use both systems simultaneously, Quoretech's *QuoreOne* and Cardios' *Cardiolight*. In this way, it will not be necessary to use any randomization technique.

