#### 3.3. Analysis Populations

All individuals of both sexes, aged 18 years or older who use both systems simultaneously for 24 hours, present complete data in both examinations and have signed the consent form will be part of the Full Analysis Set (FAS).

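### SAP 5.5 plans no safety analysis for a reason that does not fit a design adding a chest-worn test recorder, and the SAP has no systematic summary of device effects (low severity)

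*SAP*

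**What the plan says.** SAP 5.5 (Safety) is one sentence: "There will be no safety analysis, as there is no intervention in this study".

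Other sections describe the exposure:

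- SAP 2.2 says that all included patients "will use both systems simultaneously".
- SAP 1.1 calls QuoreOne the "system under test".
- Protocol 1.1 lists, among the advances of the newer recorders, "the direct positioning of the recorder on the thoracic surface". It then identifies the system in question as the one based on QuoreOne.
- SAP 2.1 describes Cardiolight as "the predominant equipment in the medical practice of the IDPC".

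The only defined analysis set (SAP 3.3) takes adults who signed consent and "who use both systems simultaneously for 24 hours, present complete data in both examinations". SAP 4.1 tabulates withdrawals and their reasons, with percentages on that same set. SAP 4.4 (Study Discontinuation/Follow-up) is marked not applicable. After removal, patients answer a questionnaire on the convenience and functions of QuoreOne (Protocol 2.5, SAP 2.1). SAP 5.2 plans lists of patient reports on convenience and a test of reported comfort.

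**The concern.** SAP 5.5 gives one reason for having no safety output, and the design contradicts it. Patients enter with an indication for a conventional 24-hour Holter. The second recorder is worn because of the study.

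What is at stake is the tolerability message, not the accuracy result. Protocol 1.2 and SAP 1.1 both say that cable-free recording makes the test better tolerated, and convenience is a secondary objective. As planned, comfort is compared among patients who completed both recordings. Nothing counts device effects, or early removals caused by a device, over everyone who wore the recorders. The device's manufacturer funds the study (Protocol 8 and 9), so readers will expect a plain statement on device effects even if there were none.

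**Working it through.** **1. Is the stated reason true of the design?**

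| Question | Source | Answer |
|---|---|---|
| Why do patients attend? | Protocol 2.2, SAP 4.2 | Indication for 24-hour Holter |
| What would they normally wear? | SAP 2.1 | Most likely Cardiolight, the clinic's main equipment |
| What does the study add? | SAP 1.1, 2.2 | QuoreOne, worn at the same time by everyone |
| Where is it worn? | Protocol 1.1, 1.2 | Directly on the chest |

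The absence of randomization (SAP 2.2) does not remove the added exposure. The reason in SAP 5.5 fails if intervention includes a device worn for the study. It survives only if the word means assigned treatment.

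**2. Where could a device effect appear?**

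- *Withdrawal reasons (SAP 4.1):* only if the effect made the patient withdraw.
- *Convenience lists (SAP 5.2):* only if the patient mentions it. The questionnaire is described as covering convenience and functions.
- *Protocol deviations (SAP 3.2):* conceivably, if an early removal is classed as a deviation. These percentages also use the Full Analysis Set.
- *Symptom reports (Protocol 2.5):* these serve to relate complaints to the electrocardiogram, not to the device.

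None of these is a systematic count of device effects.

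**3. Who is in the denominator?**

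SAP 3.3 requires 24 hours on both systems and complete data from both examinations. A patient who removes a recorder early therefore leaves the set, yet is counted in the withdrawal numerator of SAP 4.1 over that set.

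The documents give no number of early removals. Assume w fitted patients withdraw and 182 complete:

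- w = 10: planned 10/182 = 5.5%; over all fitted 10/192 = 5.2%.
- w = 20: planned 20/182 = 11.0%; over all fitted 20/202 = 9.9%.

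The numerical distortion is small. The weakness is that these patients are in no analysis set.

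**4. What would a simple count deliver?**

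The plan states no safety event rate, margin or sample size, so there is no safety figure to reproduce. The 182 comes from the accuracy endpoint (SAP 2.3): assumed accuracy (83 + 50)/146 = 0.911 against 85%. With a Wald 95% interval, success needs at least 163 of 182 agreements, and power is 80.7%, which matches the stated 80%. Power depends on the interval method, but that has no bearing here.

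Exact upper limits for zero events in n = 182:

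- one-sided 95%: 1 − 0.05^(1/182) = 1.6%
- upper limit of the two-sided 95% interval: 1 − 0.025^(1/182) = 2.0%

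Chance of seeing at least one event, 1 − (1 − p)^182, over an assumed range of true rates p:

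| p | Chance of at least one event |
|---|---|
| 0.5% | 60% |
| 1% | 84% |
| 2% | 97% |
| 5% | >99.9% |

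The 182 is the minimum with complete data, not the number fitted. If that minimum is reached, the number fitted is at least 182, and the zero-event limit is no higher than 2.0%. The limits hold only if effects were sought in every patient.

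**The case against.** The other side has a good deal to say.

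- **Low-risk, short exposure.** The recorder is non-invasive and worn for about 24 hours. The conventional system also puts electrodes on the chest, so the added exposure is incremental. No treatment is assigned and no safety objective is stated. This stands, and it limits severity.
- **A single recording has no follow-up.** Marking SAP 4.4 not applicable is understandable. Its tension with the withdrawal table in SAP 4.1 is housekeeping.
- **A reader might infer that harm goes unreported.** The documents do not support that. Withdrawal reasons and patient reports are to be presented and could show some harm. What is absent is a systematic count.
- **A reader might infer that comparability rests on detection alone.** That is true of the primary objective only. The secondary comparisons cover heart rates, ectopic beats, episode counts, examination duration and convenience, including a test of comfort.
- **A reader might infer that adverse events are not collected at all, or that the patients excluded are those who were harmed.** Neither is shown. The text of Protocol section 5 (Ethical Aspects) is not in the copy reviewed and may cover adverse events. Nothing says why any recorder would be removed early.
- **Collection is probably over.** Protocol 7 schedules collection from February to November 2021, and the protocol is version 4.0 of 25 February 2022. A new question at removal may no longer be possible. This stands, and it reduces what can be recovered.

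What remains is an inaccurate reason behind an explicit exclusion, and no planned summary of device effects in the SAP.

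**Conclusion.** The point holds in limited form. The reason given in SAP 5.5 does not fit a design in which every patient wears an added test recorder, and the SAP plans no systematic summary of device effects. Early removers fall outside the only analysis set while still being counted over it.

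Severity is low. The primary accuracy conclusion does not change, and the denominator effect is a fraction of a percentage point to about one point in the assumed examples. The gain is that the report could make a bounded statement on device effects: at most 2.0% with zero events among 182 patients, if effects were sought in all of them.

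This rests on three assumptions: QuoreOne is additional to the recorder patients would have worn anyway, as SAP 2.1 implies; the chest placement described for the newer recorders applies to QuoreOne; and any adverse-event provisions in Protocol section 5 do not already lead to a planned summary.

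**What to change.** 1. In SAP 5.5, delete the claim that there is no intervention. Replace it with a descriptive listing and count (n, %, exact 95% CI) of device-related effects, such as skin reaction or pain, and of early removals. Attribute each to QuoreOne, Cardiolight, both or unclear.
2. Use all patients fitted with the recorders as the denominator, not the Full Analysis Set, and report that number in SAP 4.1.
3. In SAP 4.4, replace the not-applicable entry with a pointer to this listing.
4. If collection is still open, add one question at the existing removal questionnaire. If it has closed, use the recorded withdrawal reasons and patient reports, and state that effects were not solicited. In that case the interval describes reported effects only and is not an upper bound on harm.
5. If Protocol section 5 contains adverse-event provisions, cross-refer to them.

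The cost is a few lines of SAP text, one listing and one small table. The downside is that attribution is imprecise when both devices are worn together, which is why the unclear category is needed. No formal test is called for.

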## 5.6. Statistical Software

[figure not shown]
All analyses and summaries will be performed using SAS™, version 9.4 or higher. The R software (R Foundation) may also be used.

## 6. AMENDMENTS

Protocol		Amendments		
Version No.	Date	Amendment no.	Protocol Section	Summary of main changes

## ADDITIONAL INFORMATION OF THE SERVICE
